6.3.1 Primary Safety Endpoints

6.3.1.1 *Adverse Events Including Secondary Surgical Interventions*

Adverse Events

The following summary tables and listings will be provided:

1. All Adverse Events (for summary tables and tables by PT (ocular) or SOC/PT (non-ocular))
 - a. Ocular by Toricity (eye-level)
 - b. Non-ocular by Toricity (subject-level)
2. All Adverse Device Effects (tables by PT (ocular) or SOC/PT (non-ocular))
 - a. Ocular by Toricity (eye-level)
 - b. Non-ocular by Toricity (subject-level)
3. All Serious Adverse Events (including Serious Adverse Device Effects (SADEs)) (tables by PT (ocular) or SOC/PT (non-ocular))
 - a. Ocular by Toricity (eye-level)
 - b. Non-ocular by Toricity (subject-level)

4. Listing of all Adverse Events (listings by PT (ocular) or SOC/PT (non-ocular))
 - a. Non-serious Ocular (eye-level)
 - b. Non-serious Non-Ocular (subject-level)
 - c. Serious Ocular (eye-level)
 - d. Serious Non-ocular (subject-level)

Summary tables, by eye and event for ocular AEs and by subject for non-ocular AEs, will be output. For ocular AEs, the table will report the number of eyes experiencing an AE and the number of adverse events for all eyes by toricity and for non-ocular AEs, the table will include the number and percentage of subjects experiencing at least one AE by toricity. Both tables will include the number and percent of AEs related to study devices and/or procedures, and the seriousness criteria for serious AEs (per the CRF). For ocular AE summary tables, the AE event outcome and action taken due to the adverse event will also be reported.

In addition, the number and percentage of all AEs will be tabulated by Preferred Term (PT) for ocular AEs and by System Organ Class (SOC) and Preferred Term (PT) for non-ocular AEs using the Medical Dictionary for Regulatory Activities (MedDRA) dictionary (Version 26.1) for all subjects. If a subject has multiple AEs with the same PT, the PT will only be counted once per subject; similarly for subjects with multiple AEs per SOC, the SOC will only be counted once per subject. AEs will be sorted alphabetically by SOC and then by decreasing total frequency by PT.

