10.4 STRATIFICATION

Performance and safety outcome measures will be stratified by the following subgroups of interest:

- PanOptix toric vs. PanOptix non-toric, where for subject-level data, subjects with at least one eye implanted with a toric IOL are considered to be in the toric group. For eye-level data, toricity is reported by each implanted eye's model. For subjects bilaterally implanted on the same day, OD is assigned as first eye, and OS is assigned as second eye

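### SAP 6.3.1.1 is inconsistent on the counting unit for the ocular adverse event tables by preferred term: labelled eye-level, but the only counting rule is once per subject

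*SAP*

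**What the plan says.** SAP 6.3.1.1 lists the AE outputs. Item 1 is headed "All Adverse Events (for summary tables and tables by PT (ocular) or SOC/PT (non-ocular", so it takes in the PT tables as well as the summaries. Items 2 and 3 are the PT tables for adverse device effects and serious AEs. Under all three items, sub-item a is "Ocular by Toricity (eye-level" and sub-item b is "Non-ocular by Toricity (subject-level".

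For the overall ocular summary, "the table will report the number of eyes experiencing an AE and the number of adverse events for all eyes by toricity".

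The next paragraph brings in both kinds of PT table in one sentence. It begins with the ocular tables ("the number and percentage of all AEs will be tabulated by Preferred Term (PT) for ocular AEs"), adds the non-ocular tables by system organ class (SOC) and PT, and closes by referring to all subjects. The counting rule follows at once: "If a subject has multiple AEs with the same PT, the PT will only be counted once per subject". The same sentence gives a matching rule for SOC.

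SAP 10.4 deals with toricity. A subject with at least one toric lens is toric in subject-level data. "For eye-level data, toricity is reported by each implanted" eye's own model. SAP 1.3.1 requires bilateral implantation and allows a toric lens in one eye with a non-toric lens in the other.

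**The concern.** Every subject has two study eyes, so a table cannot both report eyes and count a PT once per subject, unless no subject has that PT in both eyes. The text sets a unit for the table and then gives a counting rule in another unit.

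Adverse events, including cystoid macular edema and retinal detachment, are primary safety endpoints (Protocol 6.3.1.2). Protocol 6.4.1 and SAP 9 say that the descriptive results will serve for comparison with state-of-the-art thresholds. A numerator in subjects over a denominator in eyes can only lower a rate, never raise it. Two programmers who each follow the text could also produce different ocular PT tables from the same data, and could place the events of mixed-lens subjects differently between the toric and non-toric columns.

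**Working it through.** The plan states no AE rate, bilateral share or other figure that depends on this rule, so there is no figure of its own to reproduce. The check sets the passages side by side and then does the counting arithmetic.

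**Which denominator?** None is written out for the ocular PT percentages.

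- For eyes: the eye-level label in SAP 6.3.1.1; the full analysis set defined as eyes of enrolled subjects (SAP 2.1); percentages based on the analysis set or on the patients or eyes assessed (SAP 10.1); eye-level data split by each eye's own model (SAP 10.4).
- For subjects: the PT sentence refers to all subjects, and the rule counts subjects.

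Both cases therefore have to be followed through.

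**Case 1: eyes as denominator.** Let s subjects have a given ocular PT, and let a share b of them have it in both eyes.

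- Affected eyes = s(1−b) + 2sb = s(1+b).
- Counted under the rule = s.
- Counted/true = 1/(1+b), so the relative shortfall is b/(1+b). The number of eyes in the denominator cancels.

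Illustration: 100 subjects with the same lens type in both eyes (200 eyes), with s = 10 assumed. The rule always gives 10/200 = 5.0%.

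| b (assumed) | Affected eyes | Once per eye | Rule as written | Counted/true | Shortfall |
|---|---|---|---|---|---|
| 0 | 10 | 5.0% | 5.0% | 1.000 | 0% |
| 0.2 | 12 | 6.0% | 5.0% | 0.833 | 17% |
| 0.5 | 15 | 7.5% | 5.0% | 0.667 | 33% |
| 0.8 | 18 | 9.0% | 5.0% | 0.556 | 44% |
| 1 | 20 | 10.0% | 5.0% | 0.500 | 50% |

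**Case 2: subjects as denominator.** The same example gives 10/100 = 10.0% at every b. This is a sound subject-level rate with no understatement, but it is not the eye-level table that SAP 6.3.1.1 lists.

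**Mixed-lens subject.** Take a toric right eye and a non-toric left eye, with the same PT in both. By eye, SAP 10.4 puts one affected eye in each column. By subject, SAP 10.4 puts the subject in the toric group. In a table by eye with one count per subject, neither part of SAP 10.4 says which column keeps the event.

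**Scope.** The rule reaches the ocular PT tables for AEs, adverse device effects and serious AEs. It does not reach:

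- the overall ocular summary, which has its own wording in eyes and events;
- the secondary surgical intervention table (SAP 6.3.1.1) and the device deficiency table (SAP 6.3.1.2), both written in eyes;
- the AE listings, which show the eye for each ocular event.

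**The case against.** The best defence is that the rule was meant for the non-ocular tables. Its sentence goes on to SOC and the next one sorts by SOC, and only non-ocular AEs are tabulated by SOC. A programmer who follows the eye-level labels and SAP 10.4 would probably count per eye. The table shells that SAP 10.7 refers to are not in the text available here and might show that layout. This stands as a likely intention. It does not remove the conflict, because the rule comes straight after a sentence that covers both kinds of table and is not restricted.

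A second defence is that the eye denominator is an inference. That also stands: a subject denominator gives a coherent rate, and the fault is then a mismatch with the label. The passages still need to be reconciled on either reading.

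Third, the analysis is descriptive, there is no safety hypothesis (SAP 6.2), and the thresholds are given neither a value nor a unit. No changed conclusion can be shown. The listings also keep each ocular event with its eye, so bilateral events are not lost from the report.

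A reader might infer that the plan halves ocular AE rates. The documents do not support that. The halving is exact only for each subject with the PT in both eyes, and only over an eye denominator; a whole PT rate is halved only if every case is bilateral. A reader might also infer that the rule contradicts the overall ocular summary table. It does not: that table has explicit wording of its own, which the PT rule leaves unchanged.

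**Conclusion.** The inconsistency is real and is in the current SAP text. It should be fixed before the tables are programmed. It is more than a missing detail, because a stated rule conflicts with the stated unit of the table.

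What the documents establish is an inconsistent counting unit, not a built-in bias of known size. The shortfall of 0% to 50% assumes that the rule is applied to the ocular tables and that the denominator is eyes. Where it falls in that range depends on b, which the documents do not give; a PT with no bilateral cases is unaffected. The column problem arises only for mixed-lens subjects with the same PT in both eyes, and the documents do not say how many to expect.

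**What to change.** Replace the counting sentence in SAP 6.3.1.1 with two rules:

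- Ocular PT tables: an eye with several AEs of the same PT is counted once; the denominator is the number of eyes of that toricity.
- Non-ocular tables: a subject is counted once per PT and once per SOC; the denominator is the number of subjects.

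The first rule also settles the mixed-lens case, because each eye goes to the column of its own model. If a subject-level view is wanted as well, add the number of subjects with the PT in at least one eye as a separate, labelled column.

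The cost is a short SAP edit and a matching program specification. No new data are needed, because the eye is already recorded for ocular AEs, and nothing changes for sites or subjects. If counting per eye was always intended, the edit only records it.

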6.3.1.2 Device Deficiencies

The number and percentage of eyes with a device deficiency, each device deficiency description category (per CRF), and whether the device deficiency could have led to a serious adverse event will be reported separately for first implanted eye and second implanted eye (if applicable) and for all eyes by toricity. A device deficiencies listing will also be provided and includes the variables subject, age, sex, implanted eye (first eye, second eye), eye (OD/OS), study device, lens model,

days from surgery, the description of the deficiency, the circumstances that led to the device deficiency, whether the deficiency could have led to a SADE, and the medical term for the SADE.

7 INTERIM ANALYSIS STRATEGY

There are no interim analyses planned for this study.

8 FINAL ANALYSIS STRATEGY

The endpoint of interest is 3 to 5 years (+/- 90 days) post implantation. After all subjects complete their follow-up visit, the study database will be locked to conduct final analyses. A full set of output will be generated for review.

9 SAMPLE SIZE AND POWER CALCULATIONS

The study will recruit a total of 210 subjects for both AcrySof PanOptix IOL models to obtain 200 evaluable subjects (n=100 non-toric and n=100 toric). A minimum of 100 subjects bilaterally implanted with AcrySof PanOptix non-Toric should be evaluable. In addition, a minimum of 100 subjects with at least one eye implanted with AcrySof PanOptix Toric should be evaluable. Alcon will attempt to enroll all variants in the AcrySof PanOptix Toric family. ISO 22979 and ISO 11979-7 recommend a sample size of n=100 for IOLs where safety and performance risks can be adequately addressed with the sample size required of a Level B clinical investigation. Therefore, a target enrollment of up to 105 (enrolled) to achieve a goal of 100 evaluable subjects for both AcrySof PanOptix toric and non-toric models is justified by ISO standards for IOLs. Based on a pooled standard deviation of 0.07 logMAR and a t-distributed error, a sample size of 100 subjects gives an expected half width of a 95% confidence interval of 0.014 logMAR. Thus, it can be expected with 95% confidence that the estimated mean binocular BCDVA will be within 0.014 logMAR (< 1 letter on a logMAR visual acuity chart) of the true mean with a sample size of at least 100 subjects and a standard deviation of 0.07 logMAR. Descriptive results from this long-term RWE study are sufficient to provide a comparison to shorter term follow-up data of these models, and SotA safety and performance thresholds. Performance and safety outcome measures will be stratified by models (toric and non-toric).

Table 2. Subject Sample Distributions

AcrySof PanOptix Family Implants	
Toric	100
Non-Toric	100

10 STATISTICAL METHODS

10.1 STATISTICAL RULES

Appropriate descriptive statistics will be computed and presented for all categorical and continuous endpoints. For categorical variables, the number and percentage of subjects/eyes within each category of interest will be presented. The percentages will be calculated based on the respective analysis set or the number of non-missing observations (i.e., the number of patients/eyes assessed) in the respective analysis set where applicable. For categorical variables with at least one missing observation, a category of 'missing' will be added to document the number of missing

observations. If there is no missing observation, a category of ‘missing’ may not be added. Percentages will be rounded to one decimal place.

For continuous variables, the number of subjects/eyes with non-missing data, mean, standard deviation, median, minimum and maximum, and 95% CI of the mean, when applicable, will be calculated. There will be no imputation for missing data. Means and medians will be rounded to one decimal more than that with which the original data are recorded. The standard deviation will be rounded to two decimals more than the original data. Minimum and maximum values will be reported with the same number of decimals with which the original data are recorded.

Theoretical lower limits will be set for 95% CIs of the mean as follows:

- VA – -0.30
- IOP – 0.00
- Absolute Residual Cylinder – 0.00
- Misalignment – 0.0
- IOL Axis – 0.0

10.1.1 Visual Acuity

Visual acuity is measured at the immediate post-op visit (1-6 months post-op) and Visit 1 (3-5 years post-op, +/- 90 days), and other standard of care visits, when applicable [REDACTED]. Distance VA is measured per the site’s standard of care practice using charts validated for the specific testing distance. All distance VA will be converted to LogMAR scale prior to analysis.

For VA not reported in LogMAR, refer to Table 3 to convert the corresponding LogMAR VA. For example, if the distance VA is 20/25 Snellen, then the corresponding LogMAR VA is $-\log_{10}(20/25) = 0.10$.

Table 3. Distance Visual Acuity Conversion Formula Chart

Visual Acuity	LogMAR
Snellen Feet 20	$LogMAR = -\log_{10}\left(\frac{20}{\text{Snellen Visual Acuity Denominator}}\right)$

10.2 CONVENTIONS

Change in value from 1st visit to follow-up visit

For a given parameter, the change from baseline for postoperative visit, Visit X, will be calculated as:

Change: Follow-up Visit X - Baseline

Percent Change: $[(\text{Follow-up Visit X} - \text{Baseline}) / \text{Baseline}] * 100$

Days from Surgery

Days from surgery will be calculated as: (Date of the event – Date of surgery)

AE duration

End date of AE – Start date of AE + 1

10.3 MISSING DATA

No missing data imputation is planned for this study.

10.4 STRATIFICATION

Performance and safety outcome measures will be stratified by the following subgroups of interest:

- PanOptix toric vs. PanOptix non-toric, where for subject-level data, subjects with at least one eye implanted with a toric IOL are considered to be in the toric group. For eye-level data, toricity is reported by each implanted eye's model. For subjects bilaterally implanted on the same day, OD is assigned as first eye, and OS is assigned as second eye

10.5 ANALYSIS TIME POINTS

Analysis timepoints/windows will not be considered for analysis purposes. All scheduled visit data will be presented based on the visit reported in the CRF. For example, all scheduled Visit 1 data will be reported and analysed as Visit 1, regardless of the number of days the visit occurred from IOL implantation. Any visits occurring outside of a visit window should be logged as protocol deviations (PD) and reported in the PD listing.

10.6 STATISTICAL SOFTWARE

Unless otherwise specified, analyses, summary outputs, listings, and figures will be generated [REDACTED].

10.7 STATISTICAL OUTPUT

Analysis datasets will be created from the raw EDC datasets to facilitate programming of Tables, Figures, and Listings (TFL). Proposed shells for TFL will be provided as listed in the planned output (See Section 14.2). Tables and Figures will be provided in word format. Listings may be prepared in word or excel format.

11 QUALITY CONTROL AND VERSION CONTROL

The Statistical Analyst will direct the project team to apply quality control and data validation programming to ensure consistency and accuracy of the statistical analysis datasets, statistical analyses, and associated output, according to ICON standard operating procedures [REDACTED]

[REDACTED] The review involves, but is not limited to the following: generation of QC statistics, checking calculations of

derived variables, confirmation of analytic cohort, examination of the SAS® LOG or equivalent, confirmation of statistical validity, and consistency of output across tables, listings, and figures.

ICON plc will designate the initial version of the SAP approved by the Sponsor and ICON plc as Version 1.0. ICON plc will document any changes made to the SAP in a new version and the version number updated. ICON plc may complete revisions to SAP attachments without requiring additional revisions and approval to the SAP.

13 REVISION HISTORY

Version	Date	Change from Previous Version
V1.0	18Apr2025	Final SAP v1.0

14 APPENDIX

14.1 SCHEDULE OF EVENTS

Event	Retrospective		Prospective	
	Preoperative and Operative Visit	Postoperative Standard of Care & Unplanned Visits	Visit 1 (3-5 Years +/- 90 Days Postoperative)	Unscheduled Visit ^a
Informed Consent			✓	
Eligibility Determination			✓	
Demographics			✓	
Medical History	✓ ^b			
Concomitant Medications	✓***	✓	✓	✓**
Biometry & Keratometry	✓ ^c			
Preoperative Manifest Refraction	✓ ^c			
Predicted Residual Refractive Error	✓*			
Lens Model & Power	✓			
IOL Calculation Method	✓*			
Other Surgical Procedures During Cataract or Refractive Lens Exchange Surgery	✓*			

Manifest Refraction	✓*	✓*	✓	
Binocular UCDVA		✓ [†]	✓	
Monocular BCDVA		✓ [†]	✓	✓**
Binocular BCDVA		✓ [†]	✓	
Binocular UCIVA at 66 cm		✓ [†]	✓	
Binocular DCIVA at 66 cm		✓ [†]	✓	
Binocular UCNVA at 40 cm		✓ [†]	✓	
Binocular DCNVA at 40 cm		✓ [†]	✓	
Slit Lamp Examination (Biomicroscopy)	✓	✓	✓	✓**
Posterior Capsule Opacification (PCO)			✓	✓**
Capsulotomy Assessment			✓	
Tonometry			✓	✓**
Dilated Fundus Examination			✓	✓**
Actual Axis of IOL Orientation	✓*	✓ ^{††}	✓	
Assessment of Adverse Events	✓	✓	✓ ^d	✓**
Assessment of Device Deficiencies	✓*	✓*	✓	✓**
Study Exit			✓	✓**

^a Prospective visit after Visit 1 to monitor subjects with ongoing AEs

^b Medical history includes all relevant systemic and all ocular conditions that began prior to surgery and implantation of study IOL(s).

^c Preoperative keratometry, biometry, and manifest refraction assessments for each eye should have occurred within 90 days of IOL implantation of the respective eye.

^d AEs should be assessed at all postoperative visits through Visit 1 and recorded in EDC.

* If available

** As needed

*** Do not enter medications used for cataract surgery in EDC

[†] Immediate postoperative visual acuity (1-6 months postoperative), if available

^{††} From 1 day postoperative visit, if available
